5.5.2. Best Response to the Treatment at Inclusion and During Follow-up

The best response to the main treatment at inclusion with targeted therapy or other treatment (ongoing at the time of patient inclusion into the study) will be described by analysis group (targeted therapy or other treatment) then according to targeted therapy, chemotherapy and somatostatin-analogs groups.

In addition, the best response during follow-up will also be described overall.

The following ranking will be used in order to define this variable:

complete response>partial response>clinical response>stable disease>disease progression

Data will be deemed to be missing if they have not been completed, or if the "un-assessable" box is checked.

The criterion used in this analysis will be the RECIST criterion if available or the clinician's assessment if it is not.

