Examinations performed to assess the tumour (imaging and/or histology)			х	х	
Radiological and clinical responses as judged by the investigator				х	х
Safety					
Retrospective safety (adverse events that occurred prior to inclusion in the study) as described above (Table 2).			X*		
Prospective safety (all adverse events observed during the study) *Recorded for ALL prevalent case patients.				х	х

^{*}Recorded for ALL prevalent case patients.

6. Study monitoring and quality control

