9.1.3. Left truncation and left censoring

For prevalent case patients who have started their current treatment before enrolment in the study, there is left truncation bias due to the fact that it is impossible to include deceased patients in the study. Prevalent case patients all lead to left censoring bias due to the absence of retrospectively recorded tumour assessments.

These types of bias will be taken into account in the analysis of overall survival and progression-free survival through use of a statistical method that will be detailed in the statistical analysis plan.

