4.3. Analysis Sets

4.3.1. Patient Sets

- Non-included patients: all patients who are not included in the study (as recorded in the non-inclusion register).
- Included patients: all patients included in the study.
- Safety analysis set: all patients included in the study who received at least one dose of the documented treatment (the treatment start date must be entered) in the study (targeted therapy or other treatment). If the patient is prevalent, the treatment must

still be ongoing at the time of inclusion in the study and if the patient is incident, the treatment must be started at or after inclusion in the study.

• Reference set (Full Analysis Set): patients included who meet the eligibility criteria and have received at least one dose of the treatment documented during the prospective follow-up period (the treatment start date must be completed and the treatment stop date must be after the date of inclusion if the start date is prior to the date of inclusion) in the study (targeted therapy or other treatment). Patients with no follow-up data will be excluded from this population.

Two treatment groups will be analysed: the "targeted therapy" with two subgroups, everolimus (AFINITOR®) and sunitinib (SUTENT®); and an "other treatments" group with four subgroups: chemotherapy, somatostatin analogs, interferon-alpha and metabolic radiotherapy.

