- Number of right censors (with details of patients who are lost to follow-up, no disease progression/death);
- Survival (in months): median (+95% CI), Q1 (+95% CI), Q3 (+95% CI), minimum, maximum;
- Estimated survival rate at a specific time (for example 6 months, 1 year and 2 years): number of subjects at risk, survival rate at each time.

These survival rates will be estimated and described in each of the following groups and subgroups:

- Targeted therapies group (with an estimate in the Everolimus and Sunitinib subgroups);
- Other treatments group (with an estimate in the chemotherapy, somatostatin analogs, interferon alpha and metabolic radiotherapy subgroups).

Handling of truncation/left censoring:

The study includes a retrospective and/or prospective data collection period depending on whether the patient is prevalent or incident in terms of his/her tumour treatment at the time of inclusion into the study.

The time to event of interest ("survival" time) or censoring if no event occurs (right censoring) will be based on the treatment line start date at the time the patient was included into the study.

As a result, when patients are recruited into the study, those patients who have already died on treatment could not be included, whereas patients who were still alive on treatment were included. This is left truncation.

In addition, the prevalent patients included could progress before inclusion into the study and not stop the treatment started or ongoing at the time of inclusion. This progression could not be identified and is a left censoring.

In practice, after disease progression on a given treatment, the treatment is changed. As a result, prevalent patients we observed on a given treatment at inclusion could not by definition experience disease progression.

As a result, we also do not see patients on a given treatment at inclusion who progressed on the same treatment prior to entering the study and we therefore deem these cases to be left truncations.

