6.1.3. Left Truncation and Left Censoring

Left truncation bias is present for prevalent patients who started ongoing treatment prior to inclusion into the study because of the impossibility of including patients who have died into the study. The prevalent patients also exhibit left censoring bias because of the lack of retrospective collection of tumour assessment data.

These sources of bias are taken into account in the overall survival analysis and progression-free survival analysis using the statistical method described in Section 5.5.1.

Incident patients contribute to the survival curve from their baseline date. Conversely, prevalent patients are only at risk of developing an event from their inclusion into the study onwards and therefore do not contribute to the survival curve from their baseline date, although do contribute from a later date after their inclusion into the study. All patients from the reference set will therefore be taken into account into the survival analysis although patients whose treatment started two years before the beginning of the study will only be included after a two-year follow-up period and will therefore not be included in the estimation of the two-year survival rate. This is a limitation of the study.

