Using a similar template:

Table 14.2.1.3: Analysis of Progression-Free Survival – Reference Set – Targeted Therapy Groups

Table 14.2.1.4: Analysis of Progression-Free Survival – Reference Set – Other Treatments Groups

Table 14.2.1.5: Analysis of Overall Survival – Reference Set – Overall

Table 14.2.1.6: Analysis of Overall Survival – Reference Set – Targeted Therapies Group Vs Other Treatments

Table 14.2.1.7: Analysis of Overall Survival – Reference Set – Targeted Therapies Groups

Table 14.2.1.8: Analysis of Overall Survival – Reference Set – Other Treatments Groups

^{*} Event related to main treatment at inclusion.

Programmer note:

- The Kaplan-Meier curves associated with the analyses.
- Show the 95% confidence interval (log-log transformation) of the survival function for the total population analyses.

Table 14.2.1.9: Best Overall Response to the Main Treatment At Inclusion – Reference Set – Analysis Based on Targeted Therapies and Other Treatments

		Targeted therapies (N=XX)	Other treatments (N=XX)	Total (N=XX)
Best overall response	N	XX	XX	XX
•	Missing data	XX	XX	XX
	CR	XX (XX.X%)	XX (XX.X%)	XX (XX.X%)
	PR	XX (XX.X%)	XX (XX.X%)	XX (XX.X%)
	Clinical response	XX (XX.X%)	XX (XX.X%)	XX (XX.X%)
	SD	XX (XX.X%)	XX (XX.X%)	XX (XX.X%)
	PD	XX (XX.X%)	XX (XX.X%)	XX (XX.X%)

Using the same template:

Table 14.2.1.10: Best Overall Response with Main Treatment at Inclusion – Reference Set – Analysis by Treatment Subgroup

Table 14.2.1.11: Best Overall Response During Follow-Up – Reference Set

		Total (N=XX)
Best overall response	N	XX
•	Missing data	XX
	CR	XX (XX.X%)
	PR	XX (XX.X%)
	Clinical response	XX (XX.X%)
	SD	XX (XX.X%)
	PD	XX (XX.X%)

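### Best response to the inclusion treatment pools incident patients with prevalent patients whose earlier responses were not collected, so the percentages do not measure what the tables' titles say

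*SAP*

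**What the plan says.** SAP 5.5.2 plans a description of "The best response to the main treatment at inclusion with targeted therapy or other treatment", first for targeted therapy against other treatment, then for targeted therapy, chemotherapy and somatostatin analogs. The shell of Table 14.2.1.9, titled "Best Overall Response to the Main Treatment At Inclusion" (SAP 9.2), uses the reference set. Its only columns are targeted therapies, other treatments and total. Table 14.2.1.10 follows the same template by treatment subgroup.

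The reference set includes prevalent patients, on the condition in SAP 4.3.1 that the "treatment stop date must be after the date of inclusion if the start date is prior to the date of inclusion".

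On what is known before inclusion:

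- Protocol 9.1.3: "Prevalent case patients all lead to left censoring bias due to the absence of retrospectively recorded tumour assessments".
- SAP 6.1.3: "The prevalent patients also exhibit left censoring bias because of the lack of retrospective collection of tumour assessment data".
- Protocol Table 3 (section 5.2.2) has a row "Radiological and clinical responses as judged by the investigator". It is ticked only for follow-up visits and anticipated end of study.

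On who can be prevalent, SAP 5.5.1 reasons that treatment is changed after progression, so "prevalent patients we observed on a given treatment at inclusion could not by definition experience disease progression". It adds that a progression before inclusion without a treatment stop could not be identified.

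**The concern.** A best-response percentage is normally read as the best result reached at any time from the start of the line. For incident patients the plan can deliver that, because the line starts at or after inclusion and its assessments fall in the prospective period. For prevalent patients it cannot: the early part of the line, when first responses and first failures occur, is unobserved, and those who failed early are mostly absent.

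The survival analyses deal with this through delayed entry to the risk set. A simple percentage has no risk set and gets no such correction. Best response is also reported under the primary-objective heading and by treatment group, and the health authority's request (Protocol section 2, justification) was for data set against other treatments. If the groups differ in prevalent share, or in time already spent on the line, part of any visible difference between columns will come from how patients were enrolled.

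**Working it through.** **What the documents establish**

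1. *Pooling.* SAP 5.5.2 and both table shells have no incident/prevalent split.
2. *Unobserved history.* Protocol 9.1.3 and SAP 6.1.3 agree that earlier tumour assessments were not collected. Table 3 ticks tumour examinations at enrolment, but not response. In the CRF the response items belong to the tumour assessment visit (CRF 3.1), not the enrolment visit.
3. *Selection.* SAP 4.3.1 and 5.5.1 together mean that a prevalent patient is someone who had not stopped the line, and usually had not progressed on it.
4. *No remedy here.* SAP 6.1.3 says the biases are taken into account in the survival analyses. The left-truncated estimator and the incident-only supportive analysis in SAP 5.5.1 are specified for overall and progression-free survival only.

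**Which way the percentages move**

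No figure for best response is stated, so there is none to reproduce. Two mechanisms act on the prevalent patients:

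- Selection removes early progressors and favours durable responders.
- Missing history lets an earlier response or stable disease go unseen. A former responder may be recorded as stable, and a formerly stable or responding patient who progresses at the first visit after inclusion is recorded as progression.

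A simulation shows how these combine. Only the 2–3 month visit spacing comes from the protocol. Everything else is **assumed**: the true rates, the durations of response and stable disease, and pre-inclusion time uniform from 0 to a maximum. Prevalent patients are those still progression-free at inclusion, and best response is read from post-inclusion visits only.

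Progression as best response, with a 12-month maximum:

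| Assumed true progression, all starters | Primary progressors among prevalent entrants | Recorded as progression, prevalent | Selection | Missing history | Net |
|---|---|---|---|---|---|
| 15% (true response 20%) | 3.1% | 16.8% | 3.1 − 15 = −11.9 | 16.8 − 3.1 = +13.7 | +1.8 |
| 20% (true response 35%) | 4.4% | 17.7% | 4.4 − 20 = −15.6 | 17.7 − 4.4 = +13.3 | −2.3 |

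The net sign changes between two unremarkable sets of assumptions.

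Response in the first scenario: true best response among the prevalent entrants is 24.8%. The recorded figure is 8.9% if a response reached before enrolment is entered as stable disease, and 22.5% if it is still entered as a response. With prevalent share s, pooled = s × prevalent + (1 − s) × incident. At s = 0.5 and incident response 20%:

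- 0.5 × 0.089 + 0.5 × 0.200 = 0.1445
- 0.5 × 0.225 + 0.5 × 0.200 = 0.2125

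Range over s from 25% to 75%, maximum pre-inclusion time of 6, 12 or 24 months, and both recording conventions:

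| Assumed true response / progression | Pooled response | Pooled progression |
|---|---|---|
| 20% / 15% | 9.7–23.9% | 15.4–16.3% |
| 10% / 10% | 4.8–11.8% | 11.4–15.3% |
| 35% / 20% | 17.4–45.7% | 17.5–19.6% |

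These are not predictions for this study. They show only that neither sign nor size can be read off the plan.

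**The case against.** *Response may have been collected retrospectively.* Protocol 9.2 and SAP 6.2 both speak of retrospective data on response for the ongoing line. If such data existed, the gap could be closed. But those passages contradict Protocol 9.1.3 and SAP 6.1.3, and the CRF has no enrolment field in which a response could be entered. The data schedule favours the reading taken here, and the contradiction needs resolving.

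*Some earlier responses may be recovered.* The anticipated end of study form asks for best response when the patient was last seen, and SAP section 8 lists that variable as key. It is completed only for patients leaving before 24 months, so it can repair the table only in part. Separately, the CRF visit item records response to treatment in the investigator's opinion, so a maintained response can still be entered as partial or complete. That weakens any claim that responses are systematically lost.

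*The table is minor and descriptive.* This largely stands. SAP 5.5 names progression-free survival, overall survival and safety as the primary-objective parameters; no test or sample size rests on best response; SAP 6.4 cautions against treatment comparisons; and the lack of earlier assessments is a declared limitation. Readers will also see incident and prevalent counts (Table 14.1.3.1) and time from treatment start to inclusion (Table 14.1.4.1.11). None of this makes the title accurate, and neither document names best response as affected.

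*A tempting stronger reading.* A reader might infer that response is understated, progression under-counted and disease control overstated. The documents do not support a direction: that reading applies the missing history to responders alone and overlooks patients whose earlier stability or response is unseen and who are then recorded as progressing.

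**Conclusion.** The point holds as a mismatch between label and data. Tables 14.2.1.9 and 14.2.1.10 promise best response to the inclusion treatment, but for prevalent patients the plan can observe only best response after inclusion, in a group selected for still being on the line. The pooled percentages are distorted in a direction and by an amount that the documents do not determine, since they state no prevalent share, time on treatment or response rate. No bias figure should be quoted as a property of this study.

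The conclusion rests on Protocol 9.1.3, SAP 6.1.3, Table 3 and the CRF being right about what was collected. If usable retrospective response data turn out to exist, SAP 5.5.2 would have to say how they enter the derivation. The consequence is limited to a descriptive result, but the correction is cheap and should be made.

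**What to change.** 1. In SAP 5.5.2 and Tables 14.2.1.9 and 14.2.1.10, add incident and prevalent columns within each treatment group and keep the total.
2. Label the prevalent column *best response observed after inclusion*, and state that the incident column is interpreted as the estimate of best response to treatment.
3. Reconcile Protocol 9.2 and SAP 6.2 with Protocol 9.1.3, SAP 6.1.3 and the CRF on whether response before inclusion was collected.

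No new data are needed. The incident/prevalent flag already exists, and the SAP already uses the split for discontinuations (5.7.1) and for exposure by ECOG (Tables 14.3.1.10 and 14.3.1.11).

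The cost is precision in the incident column. With the planning example of 75 patients per group and a 20% response, the 95% half-width is 1.96 × √(0.2 × 0.8 / 75) = 9.1 points, matching the SAP 4.2 table. If half were prevalent (an assumption), about 37 would remain: 1.96 × √(0.2 × 0.8 / 37) = 12.9 points. Keeping the total column leaves the pooled figure available to readers who want it.

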5.6. Analysis of Secondary Objectives

The analysis of patient characteristics is shown in Section 5.4.1.

The following analysis will also be carried out in order to meet the secondary objectives of the study:

• Patient management: frequency of visits, tumour assessment methods, therapeutic management.

5.6.1. Management of Patients

The following parameters will be analysed in order to describe management of the study patients:

- Number and frequency of tumour assessment visits;
- Investigations used for the tumour assessment;
- Treatment management: changes to treatment, dose steps, concomitant treatments, number and type of treatment lines received during follow-up.

The different main treatment lines and main concomitant treatment line received by patients during the follow-up period will be listed.

The numbers and percentages of patients who received a treatment at least once during the study will be described by analysis group (targeted therapy or other treatment) and for each type of study treatment (everolimus, sunitinib, somatostatin analogs, chemotherapy, metabolic radiotherapy or interferon-alpha) in the reference and safety analysis sets. The numbers and percentages of patients receiving a combination at least once during the study will also be described, with details of the combinations. An "other treatments" category will be created for combinations other than the study treatment.

5.7. Safety

Safety assessment criteria will be used to:

- Treatment discontinuations and reasons for this,
- Adverse events and any complications recorded prospectively (graded according to the 'Common Terminology Criteria for Adverse Events' (CTCAE) version 4.0, dated May 2009).

These criteria will be shown descriptively in the safety analysis set.

The analyses of adverse events will be performed twice on the safety analysis set:

- by treatment group at inclusion;
- by group in which treatment was received at least once during the study. In this analysis, the AE will be attributed to ongoing treatment at the start of the AE. An AE beginning after a treatment was discontinued could be attributed to the treatment depending on the rules shown in the table below.

Prior to the safety analysis, the number of patients who received the treatment at least once in the group (targeted therapy/other treatments) and in the treatment subgroups will also be presented. Exposure for each treatment group and subgroup will be calculated.

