3.1. Primary objective

The primary objective of this observational study is to describe the real-world outcomes in adult patients treated (targeted therapies and other treatments) for a well-differentiated, unresectable or metastatic, progressive pancreatic neuroendocrine tumour in terms of morbidity and mortality at 2 years. The following parameters will be assessed in order to meet this objective:

- Rate of progression-free survival at 2 years. Progression-free survival is defined as the time between the start of treatment (of the treatment line ongoing at the time the patient was enrolled in the study) and the date of the first disease progression or death, irrespective of the cause.
- Overall survival at 2 years. Overall survival is defined as the time between the start of treatment (of the treatment line ongoing at the time the patient was enrolled in the study) and death, irrespective of the cause.
- Safety of the treatments (targeted therapies and other treatments) defined by instances of treatment discontinuation and the reasons, adverse events (graded according to the 'Common Terminology Criteria for Adverse Events' (CTCAE) version 4.0 of May 2009), and any complications of adverse events.

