It is important to note that statistical comparisons in the strictest sense between the different treatment groups in this observational study are not appropriate due to the expected bias and because the groups are not comparable at enrolment (treatments not assigned randomly). If, however, comparisons are envisaged, a multivariate Cox model will be used in order to adjust for patient characteristics that may potentially be associated with the type of treatment received and survival and that could be liable to skew the estimates (confounding factors, effect modification).

 Safety of the treatments (targeted therapies and other treatments) during the prospective phase of the study, defined by instances of treatment discontinuation and the reasons for this, adverse events (graded according to the 'Common Terminology Criteria for Adverse Events' (CTCAE) version 4.0 of May 2009), and any complications of adverse events.

The proportion of patients for whom adverse events are reported (total proportion and proportion reporting grades 3 or 4 adverse events) will be estimated as well as the proportion who stop treatment due to an inability to tolerate it.

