				□ Resolved If resolved, Date of resolution:// □ Resolved with sequelae If resolved, Date of resolution:/ □ Resolution ongoing □ Not resolved □ Unknown	□Severe	□ Grade 1 □ Grade 2 □ Grade 3 □ Grade 4 □ Grade 5	□ Serious □ Not serious	treatment If related, please state: Related to Sunitinib	temporarily ☐ Stopped definitively		

Observational study protocol final version of 17/07/2018

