5.5. Analysis of the Primary Objective

The following parameters will be analysed in the reference set in order to meet the primary objective of the study:

• Progression-free survival at 2 years when receiving the main treatment at the time of inclusion. Progression-free survival is defined by the time between starting treatment (the sequence ongoing at the time of patient inclusion into the study) and the date of

first documented disease progression or all-cause death when receiving the main treatment at the time of inclusion.

- Overall survival rate at 2 years. Overall survival is defined by the time between starting treatment (the sequence ongoing at the time of patient inclusion into the study) and all-cause death.
- Treatment safety (targeted therapies and other treatments) during the prospective period of the study described in terms of treatment discontinuations and the reasons for these, adverse events (graded according to CTCAE version 4.0, May 2009) and any complications of these adverse events. This analysis is described in Section 5.7.

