Listing 16.2.10: Adverse Events Suspected to be Related to the Study Treatment Leading to Permanent Discontinuation of Treatment

LISTING 16.2.11: Adverse Events Suspected to be Related to the Study Treatment Leading to Temporary Discontinuation of Treatment

^[2] Recovered, recovered with complications, currently recovering, subject not recovered, unknown.

^[3] Mild, moderate, severe.

^{[4] 0, 1, 2, 3, 4, 5.}

^[5] Temporary discontinuation, permanent discontinuation, increase of dosage, reduction of dosage, continued unchanged, unknown, not applicable.

Listing 16.2.12: Deaths

Patient Sex Age	- Safety analysis set - Reference set	Date of death	Reason for death	Details if Other
XXXXX	Yes/No	DDMMYYYY	Related to the	XXXXXXXXXXXXXXXXX
XXXXX	Yes/No		disease/Related to treatment	
XX			/Other	

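### Complications of adverse events belong to the primary safety objective, but the SAP plans no count or percentage by treatment for any adverse event outcome except death

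*SAP*

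**What the plan says.** Protocol 3.1 defines treatment safety, one of the three primary parameters, by discontinuations and their reasons, CTCAE-graded AEs, "and any complications of adverse events". Protocol 8.3.2.1 repeats the definition for the prospective phase. It then names the estimates to be produced, starting with "The proportion of patients for whom adverse events are reported", then the grade 3 or 4 proportion and the proportion stopping because of intolerance. It names no estimate for complications.

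SAP 5.5 carries the component into the primary objective and points onward: "any complications of these adverse events. This analysis is described in Section 5.7". SAP 5.7 has two bullets, discontinuations with reasons and "Adverse events and any complications recorded prospectively", followed by the commitment "These criteria will be shown descriptively in the safety analysis set".

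The prospective AE table of the CRF has an outcome field, one of whose categories is "Resolved with sequelae". In the SAP the outcome appears as a column of Listing 16.2.6, with categories "Recovered, recovered with complications, currently recovering, subject not recovered, unknown". Listings 16.2.7 to 16.2.11 use the same template.

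**The concern.** The objective names a component, SAP 5.5 says Section 5.7 describes its analysis, and 5.7 promises a descriptive presentation. The detailed specification in 5.7.2 and the table shells then leave it out. SAP 5.8, which records departures from the statistical part of the protocol, mentions only the confidence-interval method, so this looks like an oversight and not a decision.

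At stake is the reporting of non-fatal lasting harm by treatment. The study answers a health-authority request to describe morbidity and mortality at two years. Whether an AE left sequelae is a natural part of morbidity, and grade and action on treatment do not show it: a grade 3 event that clears completely and one that leaves sequelae fall in the same grade 3 row. All other AE characteristics in 5.7.2 get numbers and percentages of patients. This one gets only a listing, from which a reader would have to count by hand.

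**Working it through.** **Is there a summary anywhere?** The objective was traced through to the planned outputs.

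| Step | Place | Complications or AE outcome? |
|---|---|---|
| Objective | Protocol 3.1, 8.3.2.1; SAP 5.5 | Named |
| Criterion | SAP 5.7 | Named, with a promise to describe |
| Data collected | CRF, prospective AE table | Outcome field with five categories, one for sequelae |
| Patient-level characteristics | SAP 5.7.2 | Any, serious, related, fatal, action on treatment, grade; the only outcome is death |
| Overview of AEs | Table 14.3.2.1 | 12 rows of the at-least-one type; the only outcome is death |
| Overview of grade 3 or higher AEs | Table 14.3.2.2 | 18 such rows; the only outcome is death |
| By SOC and PT | Tables 14.3.2.3 to 14.3.2.15 | 13 tables by relatedness, grade, seriousness, discontinuation and death; none by other outcome |
| Listings | 16.2.6 to 16.2.11 | Outcome column for each event |
| Key eCRF data | SAP section 8 | AE description, seriousness, relationship, death, action, grade; no outcome variable |

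The contents list in SAP section 7 runs without a gap from Table 14.3.2.1 to 14.3.2.15, so no AE table is hidden by removed text.

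**What could the term mean?** Neither document defines it. The CRF categories are resolved, resolved with sequelae, resolution ongoing, not resolved and unknown. The listing categories are the five in the quotation under what the plan says. Matched in order, the CRF's sequelae category is the listing's recovered-with-complications category. That is the only place where the SAP attaches the word to a recorded field. Reading complications as sequelae is therefore an inference, but one the SAP's own label supports. Unresolved events are a separate category in both lists, and the label gives no support for including them.

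**Would a proportion be informative?** The formula in SAP 4.2, n = (ε²/i²)·p(1−p), gives i = ε·√[p(1−p)/n]; take ε = 1.96 for 95%.

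First the plan's own figures at n = 75:
- p = 0.10: 1.96 × √(0.09/75) = 1.96 × 0.0346 = 0.068, or 6.8 points, as in the SAP 4.2 table.
- p = 0.20: 1.96 × √(0.16/75) = 1.96 × 0.0462 = 0.091, or 9.1 points, as in the table.

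Then for one targeted drug at its planned minimum of 35 patients (Protocol 5.1; SAP 3.3):
- p = 0.10: 1.96 × √(0.09/35) = 1.96 × 0.0507 = 0.099, or 9.9 points.
- p = 0.20: 1.96 × √(0.16/35) = 1.96 × 0.0676 = 0.133, or 13.3 points.

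The 10% and 20% are assumptions; the documents give no expected rate. At n = 35 and 10% only 0.10 × 35 = 3.5 patients are expected, so the normal approximation is rough there.

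**The case against.** The strongest reply is that the information is already reported. Listing 16.2.6 and the five built on its template show each event's outcome, and a yes/no column separates prospective from retrospective events. Fatal AEs are tabulated. A reader might infer from the missing tables that this part of the objective gets no result at all. The listings rule that out: what is missing is a summary by treatment.

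Second, the term is undefined. SAP 5.7 places complications in the same bullet as AEs and attaches CTCAE grading to it, so a complication could be a further graded event, already in every AE table. It could also mean consequences such as death, dose change or discontinuation, which are tabulated. Both readings are possible, so sequelae cannot be presented as the only meaning. But if one of the others was intended, the SAP should say so.

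Third, Protocol 8.3.2.1 specifies no estimate for complications, so the SAP drops nothing the protocol spelled out. This is true, but the commitment to describe the criteria is the SAP's own.

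Fourth, a reader might infer that a drug with reversible toxicity would look the same as one leaving permanent damage. The documents do not support this. Protocol section 7 makes persistent or significant incapacity a seriousness criterion, so such events enter the serious AE rows, and the fatal, grade 4 or higher and permanent-discontinuation rows also help to separate drugs. Sequelae that do not meet a seriousness criterion still go uncounted.

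Fifth, absence from the section 8 key data is weak evidence. That table also omits the AE onset date, which 5.7.2 needs for attribution.

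**Conclusion.** The point holds as a gap in summary, not in collection or listing. A named component of the primary safety objective has no planned count or percentage by treatment, although SAP 5.7 promises a descriptive presentation and the field is in the CRF. Of 15 AE tables, none covers a non-fatal outcome. Survival results and the other safety outputs are unaffected, so this is a change that should be made, not one on which the study depends.

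The conclusion rests on reading complications as AE outcome with sequelae, which the listing label supports but no definition confirms. It does not extend to unresolved events, whose frequency depends on how long each patient was followed. On the assumed proportions of 10% to 20%, the summary would carry a 95% half-width of about 7 to 9 points per treatment group if 75 are enrolled in each, and about 10 to 13 points per targeted drug at 35. That is adequate for description by group and coarse by drug.

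**What to change.** 1. In SAP 5.7, define complications, for example as an AE outcome of resolved with sequelae on the CRF, and state that this is the category labelled recovered with complications in the listings.
2. In SAP 5.7.2 and Tables 14.3.2.1 and 14.3.2.2, add the number and percentage of patients with at least one AE resolved with sequelae, by treatment, for prospective AEs in the safety analysis set. Add the same row for AEs suspected to be related.
3. Give the new rows an entry in the attribution table of 5.7.2. The existing rules for any AE (exposure plus 28 days) and for related AEs (causality column) can be carried over. Show how many AEs have a missing or unknown outcome, since the missing-data rule there covers only seriousness and causality.
4. Add the AE outcome variable to the key data in SAP section 8.
5. Optionally, add a separate row for AEs not resolved at last news, with a note that it depends on length of follow-up.

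The cost is a definition, a few table rows and one line in section 8. It needs no new data and no change to the CRF or to patient care.
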